Abbreviation or special term	Explanation
ILC2s	Type 2 innate lymphoid cells
IP	Investigational product
ITT	Intent-to-treat
L	Liter
LABA	Long-acting beta agonist(s)
LAMA	Long-acting muscarinic antagonist(s)
LTRA	Leukotriene receptor antagonist(s)
LVEF	Left ventricular ejection fraction
mAb	Monoclonal antibody(ies)
MRD	minimum required dilution
mRNA	Messenger RNA
NC	Not calculable
NQ	Not quantifiable
NR	Not reportable
NS	No sample
NT-proBNP	N-terminal prohormone of B-type natriuretic peptide
OCS	Oral corticosteroid(s)
PA	Primary analysis
PCR	Polymerase chain reaction
PD	Pharmacodynamic(s)
PEF	Peak expiratory flow
PHL	Potential Hy's law
PK	Pharmacokinetic(s)
PRO	Patient reported outcome
CCI	CCI
SABA	Short-acting bronchodilator
SAE	Serious Adverse Event
SAP	Statistical Analysis Plan
SARS-CoV-2	Severe acute respiratory syndrome coronavirus 2
SBP	Systolic blood pressure
SC	Subcutaneous
SD	Standard deviation
SGRQ	St George's respiratory questionnaire
SNOT-22	Sino-nasal outcome test
CCI	CCI
SOA	Schedule of activities

Abbreviation or special term	Explanation
SOC	System Organ Class
sST2	Soluble suppression of tumorigenicity 2
SV	Study visit
TBL	Total bilirubin
TSLP	Thymic stromal lymphopoietin
ULN	Upper limit of normal
URC	Unblinded review committee
VAS	Visual analogue scale

AMENDMENT HISTORY

Category*: Change refers to	Date	Description of change	In line with the CSP?	Rationale
Other	31 Aug 2022	
 • Rearranging of the study endpoints to mimic the CSP • Removal of text regarding airway hyperresponsiveness and remodelling (previously a sub-study); • Change to accommodate not capping randomisation of participants not included in exploratory cough sub-study solely to achieve target sample size of the sub-study; • Introduction of the 'All randomised subject' population • Additional text added about derivation rules for actual arm; • Additional text added to clarify the meaning of 'detectable serum concentration measurement post first dose' for PK population; • Analysis visit windows for parameters previously missed have been added together with the definition of the analysis phases; • Minor adjustments on imputation rules for missing data and on PK concentration data presentation; • Additional text added to clarify the derivation rules for analysis subgroups; • Adjustments on the definition of the treatment emergent adverse events (TEAE); • Clarification around AE of special interest; • Additional text added to clarify the derivation and presentation of summary statistics; • Additional text added to clarify the fixed effects to be used in the ANCOVA, MMRM and the back-up solutions in case of non-convergence; 	Y	CSP amendment v1 to v4; Improvements resulting from study team discussions and reviews.

		
 • Additional text added to clarify the reportable results for variables log-normally distributed; • Removal of representation of lab measurements outside predefined criteria as no predefined criteria are available; • Removal of statistical analysis on methacholine challenge testing and inspiratory/ixpiratory CT imaging as no more required; • Additional text added to introduce the primary analysis; • Shift tables for minimum values of haematology and chemistry laboratories from baseline have been added; • The recovery time formula related to asthma CompEx events occurred during the intervention and follow-up combined period has been corrected due to a previous mistake; • Clarification on rolling windows of time for asthma CompEx has been added; • An additional spirometry parameter (FEF25-75%) will be explored. 		
Other	10 jan 2023	
 • Added 4 PD biomarkers analyses (section 4.2.8.2 Analysis of blood biomarkers) • Added that also for the eosinophils the values will be log transformed prior to the analysis • Modified ECG normal ranges table 	Yes	Missing 4 PD biomarkers in previous version

* Pre-specified categories are

Primary or secondary endpoints; Statistical analysis method for the primary or secondary endpoints; Derivation of primary or secondary endpoints; Multiple Testing Procedure; Data presentations; Other

1 STUDY DETAILS

1.1 Study objectives

Table 1 Objectives and Endpoints

Objective	Endpoint
Primary	
To assess the effect of MEDI3506 compared with placebo on lung function, in adult participants with uncontrolled moderate-to-severe asthma.	As measured in clinic, change from baseline to Week 16 in pre-BD FEV ₁ (L).
Secondary	
To further assess the effect of MEDI3506 compared with placebo on lung function, in adult participants with uncontrolled moderate-to-severe asthma.	As measured in clinic, change from baseline to Weeks 8 and 16 in post-BD FEV ₁ (L).
To assess the PK of MEDI3506 in adult participants with uncontrolled moderate-to-severe asthma.	Serum MEDI3506 concentration-time profiles during the intervention and follow-up periods.
To assess the immunogenicity of MEDI3506 in adult participants with uncontrolled moderate-to-severe asthma.	ADA during the intervention and follow-up periods.
To assess the effect of MEDI3506 compared with placebo on asthma control in adult participants with uncontrolled moderate-to-severe asthma.	Change from baseline to Week 16 in ACQ-6 score. Proportion of participants with a decrease in ACQ-6 score of ≥ 0.5 from baseline to Week 16. Proportion of participants achieving ACQ-6 well controlled status (defined as ACQ-6 score ≤ 0.75 at Week 16).
To assess the effect of MEDI3506 compared with placebo on health status in adult participants with uncontrolled moderate-to-severe asthma.	Change from baseline to Week 16 in SGRQ score. Proportion of participants with a decrease in SGRQ total score of ≥ 4 points from baseline to Week 16.
To assess the effect of MEDI3506 compared with placebo on CompEx in adult participants with uncontrolled moderate-to-severe asthma.	Time to first CompEx event based on the period from baseline to Week 16. CompEx annualised event rate.
To assess the effect of MEDI3506 compared with placebo on concentration of FeNO in adult participants with uncontrolled moderate-to-severe asthma.	Percent change from baseline to Week 16 in concentration of FeNO in exhaled breath.

Table 1 Objectives and Endpoints

Objective	Endpoint
Safety	

To assess the safety and tolerability of MEDI3506 compared with placebo, in adult participants with uncontrolled moderate-to-severe asthma.
	
During the intervention and follow-up periods:
 
 • AEs, SAEs, AESIs • Vital signs • Clinical chemistry, haematology, and urinalysis • ECGs • LVEF as measured by echocardiogram • NT-proBNP • Number of participants seropositive for SARS-CoV-2 at end of study who were seronegative at randomisation visit • For participants testing positive for SARS-CoV-2 (by PCR or serology test), during the intervention and follow-up periods, the number and proportion of patients with COVID-19 AEs/SAEs and the proportion asymptomatic.
Exploratory	

To further assess the longitudinal effect of MEDI3506 compared with placebo on lung function in adult participants with uncontrolled moderate-to-severe asthma.
	
As measured at home, change from baseline up to Week 24 in 2-weekly mean PEF and FEV₁

To assess the effect of MEDI3506 compared with placebo on airway hyperresponsiveness in adult participants with uncontrolled moderate-to-severe asthma.
	
Change from baseline to Weeks 8 and 16 in FEV₁% reversibility.

To assess the effect of MEDI3506 compared with placebo on asthma related inflammatory blood biomarkers in adult participants with uncontrolled moderate-to-severe asthma.
	
Change from baseline to Weeks 1, 4, 8, 12, 16, 20 and 24 in inflammatory blood biomarker levels, including but not limited to:
 
 • CCI • Serum IL-5.* • Serum IL-13.* • Serum TSLP.* 
Change from baseline to Weeks 4, 16, and 24 in plasma EDN.
 
Change from baseline to Weeks 16 and 24 in total IgE.
 
Change from baseline to Week 16 in:
 
 • sST2. • Proinflammatory gene signatures in whole blood.*

Table 1 Objectives and Endpoints

Objective	Endpoint
To assess the longitudinal effect of MEDI3506 compared with placebo on small airway function in adult participants with uncontrolled moderate-to-severe asthma.	Change from baseline to Weeks 1, 4, 8, 12, and 16 in airway reactance and resistance as assessed by AO parameters, including but not limited to: 
 • R5 • R20 • R5-R20 • AX
To assess the longitudinal effect of MEDI3506 compared with placebo on lung function in adult participants with uncontrolled moderate-to-severe asthma.	As measured in clinic, change from baseline in pre-BD FEV1 to Weeks 1, 4, 8, 12, 20, and 24.
To assess the acute effect of MEDI3506 compared with placebo on pre-BD FEV1 in adult participants with uncontrolled moderate-to-severe asthma.	As measured in clinic, change in pre-BD FEV1 (L) from pre-administration of study intervention to 4 hours post-administration of MEDI3506 or placebo at Day 1.
To assess the effect of MEDI3506 compared with placebo on asthma control in adult participants with uncontrolled moderate-to-severe asthma.	During the intervention period (baseline to Week 16): 
 • Annualised rate of asthma exacerbations. • Annualised rate of hospitalised asthma exacerbations.
To assess the longitudinal effect of MEDI3506 compared with placebo on asthma control and health status in adult participants with uncontrolled moderate-to-severe asthma.	Change from baseline to Weeks 1, 4, 8, 12, and 24 in ACQ-6 score. Change from baseline to Weeks 4, 12, and 24 in SGRQ score. Change from baseline up to Week 24 in 2-weekly mean daily rescue medication usage (puffs/day). Change from baseline to Weeks 4, 8, 12, 16, 20, and 24 in: 
 • Asthma symptom score. • Mean number of night-time awakenings.
To assess the benefit-risk profile of MEDI3506 as perceived by adult participants with uncontrolled moderate-to-severe asthma.	PGI-BR at Week 16.
CCI [REDACTED]	CCI [REDACTED]
To assess the effect of MEDI3506 compared with placebo on asthma related inflammatory airway biomarkers in adult participants with uncontrolled moderate-to-severe asthma.	Percent change from baseline to Weeks 1, 4, 8, 12, 16, 20, and 24 in concentration of FeNO. Change from baseline to Weeks 4, 8, 12, 16, 20, and 24 in exploratory biomarkers measured in nasal lining fluid.* Change from baseline to Week 16 in mRNA nasal transcriptome.*

Table 1 Objectives and Endpoints

Objective	Endpoint
To assess the effect of MEDI3506 compared with placebo on nasal symptom control in a subset of adult participants with uncontrolled moderate-to-severe asthma who have comorbid CRS.	Change from baseline to Weeks 1, 4, 8, 12, and 16 in SNOT-22 score.
Exploratory cough sub-study	
To evaluate the effect of MEDI3506 compared with placebo on objective cough measures in adult participants with uncontrolled moderate-to-severe asthma	Change from baseline to Week 16 in: 
 • Daily (ie, 24 hour) cough frequency. • Awake time cough frequency. • Night-time cough frequency. • Cough VAS.

ACQ-6 = asthma control questionnaire-6; ADA = anti-drug antibody(ies); AE = adverse event; AESI = adverse event of special interest; AO = airwave oscillometry; BD = bronchodilator; COVID-19 = coronavirus disease 2019; CompEx = composite endpoint for exacerbations of asthma; CRS = chronic rhinosinusitis; ECG = electrocardiogram; EDN = eosinophil derived neurotoxin; FeNO = fractional exhaled nitric oxide; FEV₁ = forced expiratory volume in the first second; IgE = immunoglobulin E; IL = interleukin; L = litre(s); LVEF = left ventricular ejection fraction; mRNA = messenger RNA; NT-proBNP = N-terminal prohormone of B-type natriuretic hormone; PCR = polymerase chain reaction; PEF = peak expiratory flow; PGI-BR = patient global impression of benefit/risk; PK = pharmacokinetic(s); SAE = serious adverse event; SARS-CoV-2 = severe acute respiratory syndrome coronavirus 2; SGRO = St George's respiratory questionnaire; SNOT-22 = sino-nasal outcome test-22; **CCI**; sST2 = soluble ST2; TSLP = thymic stromal lymphopoietin; VAS = visual analogue scale. * **These endpoints will not be included in the CSR.**

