4.2.8.2 Analysis of blood biomarkers

Analysis of blood eosinophils

Blood eosinophils count will be summarised with descriptive statistics at each visit and change from baseline summarised for each post-baseline visit for the ITT population. Change from baseline in blood eosinophils will be analysed using MMRM as described in Section 4.1.2 for the ITT population. Endpoints will be log transformed prior to analysis. Estimates of the least square mean change from baseline for each treatment, and the difference between them, together with two-sided 80% confidence interval and one-sided p-values, will be obtained from the model for each visit. LS Mean change from baseline and two-sided 80% CI for each visit through Week 24 in blood eosinophils will be presented in figure.

Blood eosinophils count will be also summarised in shift tables comparing maximum value during treatment to baseline value for the ITT population.

Other exploratory biomarkers

The following serum and plasma biomarkers will be collected and summarised:

- Total IgE, allergen-specific IgE, sST2 (serum);
- Plasma EDN;
- CCI
- Serum IL-5;
- Serum IL-13;
- Serum TSLP.

Allergen-specific IgE status and Serum IL33:ST2 at baseline will be used for subgroup analysis of the primary endpoint (pre-BD FEV₁) as described in Section 4.2.4.3. The subgroup cut-off for Serum IL33:ST2 is the Serum IL33:ST2 baseline median.

All the above biomarkers, except allergen specific IgE will be summarised with descriptive statistics at each visit and change from baseline summarised for each post-baseline visit. Change from baseline in all the above biomarkers, except allergen specific IgE and Serum IL33:ST2 will be analysed using a MMRM as described in Section 4.1.2. Endpoints will be log transformed prior to analysis. LS Mean change from baseline and two-sided 80% CI for each analysed visit will be presented in figures.

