14.2 Exploratory Biomarker Outcome		
Table 14.2.12.1	Plasma EDN by visit, summary statistics	ITT population
Table 14.2.12.2	Percent and relative change from baseline through Week 24 in plasma EDN treatment comparisons, MMRM	ITT population
Figure 14.2.12	Percent change from baseline through Week 24 in plasma EDN, LSMeans (80% CI)	ITT population
Table 14.2.13.1	Total IgE by visit, summary statistics	ITT population

Table 14.2.13.2	Percent and relative change from baseline through Week 24 in total IgE treatment comparisons, MMRM	ITT population
Figure 14.2.13	Percent change from baseline through Week 24 in total IgE, LSMMeans (80% CI) (ITT population)	ITT population
Table 14.2.14.1	sST2 by visit, summary statistics	ITT population
Table 14.2.14.2	Percent and relative change from baseline to Week 16 in sST2 treatment comparisons, ANCOVA	ITT population

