14.2 Exploratory PD Biomarker		
Table 14.2.21.1	Serum IL-5 by visit, summary statistics	ITT population

Table 14.2.21.2	Percent and relative change from baseline through Week 16 in serum IL-5 treatment comparisons, MMRM	ITT population
Figure 14.2.21.1	Percent change from baseline through Week 16 in serum IL-5, LSMeans (80% CI)	ITT population
Table 14.2.22.1	Serum IL13 by visit, summary statistics	ITT population
Table 14.2.22.2	Percent and relative change from baseline through Week 16 in serum IL13 treatment comparisons, MMRM	ITT population
Figure 14.2.22.1	Percent change from baseline through Week 16 in serum IL13, LSMeans (80% CI)	ITT population
Table 14.2.23.1	Serum IL33:ST2 by visit, summary statistics	ITT population
Table 14.2.23.2	Change from baseline through Week 16 in pre-BD FEV1(as measured in clinic) treatment comparisons by IL33:ST2 subgroups, MMRM	ITT population
Figure 14.2.23.1	Change from baseline through Week 16 in pre-BD FEV1 measured in the clinic, LSMeans (80% CI) by IL33:ST2 subgroups	ITT population
Table 14.2.24.1	Serum TSLP by visit, summary statistics	ITT population
Table 14.2.24.2	Percent and relative change from baseline through Week 16 in serum TSLP treatment comparisons, MMRM	ITT population

Figure 14.2.24.1	Percent change from baseline through Week 16 in serum TSLP, LSMeans (80% CI)	ITT population

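### The SAP marks serum IL-5, IL-13 and TSLP as not for the CSR yet lists section-14 outputs for them, and compares arms only to Week 16 although the endpoint runs to Week 24

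*SAP*

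**What the plan says.** Protocol Table 4 and SAP Table 1 give the same exploratory endpoint, "Change from baseline to Weeks 1, 4, 8, 12, 16, 20 and 24 in inflammatory blood biomarker levels", and name serum IL-5, IL-13 and TSLP under it. In SAP Table 1 each of the three carries an asterisk, and the footnote to that table reads "These endpoints will not be included in the CSR".

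SAP 4.2.8.2 lists the same three among the biomarkers to be summarised. It plans descriptive statistics at every visit and then says "Change from baseline in all the above biomarkers, except allergen specific IgE and Serum IL33:ST2 will be analysed using a MMRM", after log transformation. It sets no time horizon for that model; the figures are to show whichever visits are analysed.

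Appendix C, the list of tables, figures and listings, has entries for all three analytes under section-14 numbering. The descriptive tables have no time limit, for example "Serum IL-5 by visit, summary statistics". The model tables do:

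- Table 14.2.21.2: "Percent and relative change from baseline through Week 16 in serum IL-5 treatment comparisons, MMRM"
- Table 14.2.22.2: "Percent and relative change from baseline through Week 16 in serum IL13 treatment comparisons, MMRM"
- Table 14.2.24.2: "Percent and relative change from baseline through Week 16 in serum TSLP treatment comparisons, MMRM"

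The matching LS-mean figures also stop at Week 16. By contrast, Table 14.2.12.2 is "Percent and relative change from baseline through Week 24 in plasma EDN treatment comparisons, MMRM".

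The SAP amendment history records that four PD biomarker analyses were added to 4.2.8.2 on 10 January 2023 because they had been missing.

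**The concern.** There are two separate problems.

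The first is reporting status. One part of the SAP excludes these three analytes from the CSR and another schedules outputs for them. A reader of the CSR could not tell whether their presence or absence was planned. Sponsor staff are unblinded at the primary analysis lock (SAP 4 and 5), so a contradiction left standing until then can be resolved either way once results are known.

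The second is the visit horizon. The endpoint names seven post-baseline visits, but the listed between-arm comparisons cover five. The two left out are the only scheduled visits after the SAP's on-treatment phase, so no model-based treatment difference would be produced for these cytokines during follow-up, although the endpoint names those visits and blood is drawn at them.

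**Working it through.** The plan states no figure to reproduce here. The check sets the texts against each other and counts visits.

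**1. Do the data and windows exist at Weeks 20 and 24?** Yes. Protocol Table 2 schedules serum exploratory biomarkers at SV11 and SV12. SAP Table 3 of section 3.1.4 gives them analysis windows of Days 128 to 155 (Week 20) and Day 156 onward (Week 24). SAP 4.1 says that the final analysis uses all data collected up to the final lock, so the timing of the primary analysis does not force a Week 16 cut.

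**2. Which visits are compared?**

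- Endpoint visits: 1, 4, 8, 12, 16, 20, 24 = 7.
- Visits within the Week 16 titles: 1, 4, 8, 12, 16 = 5.
- Not compared: 7 − 5 = 2 (Weeks 20 and 24), and 2/7 = 29% of the endpoint's visits.
- Contrasts not produced: 3 analytes × 2 visits × 2 doses versus placebo = 12, out of 3 × 7 × 2 = 42.

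**3. Where do those visits fall?** SAP 3.5.2 shows administration at SV4, SV7, SV8 and SV9, so the last dosing visit is SV9, Day 85. Week 20 is (141 − 85)/7 = 8 weeks later and Week 24 is (169 − 85)/7 = 12 weeks later. The on-treatment phase ends 28 days after the last dose, at Day 85 + 28 = 113, which is the scheduled Week 16 day. Weeks 20 and 24 are therefore post-dosing follow-up visits for a participant dosed on schedule.

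**4. Do comparable markers stop at Week 16?**

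| Marker | Appendix C comparison | Horizon |
|---|---|---|
| Plasma EDN | 14.2.12.2 | Week 24 |
| Total IgE | 14.2.13.2 | Week 24 |
| FeNO | 14.2.15.3 | Week 24 |
| Blood eosinophils | 14.3.8.7.2 | Week 24 |
| sST2 | 14.2.14.2 | Week 16 |
| Serum IL-5, IL-13, TSLP | 14.2.21.2, 14.2.22.2, 14.2.24.2 | Week 16 |

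The sST2 table stops at Week 16 because its endpoint is defined at Week 16 only. For the three cytokines the table is shorter than the endpoint.

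**5. Is the asterisk honoured elsewhere?** The other legibly starred endpoints in SAP Table 1 are the whole-blood gene signatures, the nasal lining fluid biomarkers and the nasal mRNA transcriptome. None has an entry in Appendix C. One item in the same list as the cytokines is redacted and cannot be checked. Where the SAP means work to fall outside the outputs or the CSR it says so: post-hoc subgroup identification in 3.1.7 and population PK in 4.2.8.1.

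**6. Does the text suggest how this arose?** The January 2023 revision added the PD biomarker analyses. Section 3.6.6 still lists only EDN, total IgE, sST2 and allergen-specific IgE. Asterisks left unrevised at that point would explain the pattern, but this is an inference.

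**The case against.** The best reply has four parts.

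- **Weeks 20 and 24 are not lost.** The by-visit summary tables and the text of 4.2.8.2 carry no Week 16 limit, so descriptive results at both visits are planned. This stands and confines the point to the treatment comparisons and LS-mean figures.
- **Appendix C never says CSR.** It is headed as a TFL contents list, and the SAP allows some work outside the CSR. This stands in part: the CSR reading rests on the section-14 numbering and on the pattern in step 5, which make it likely but not explicit.
- **Nothing in the protocol was changed.** Protocol 9.4.5.2 names models for eosinophils, EDN, total IgE and neutrophils and leaves other biomarkers to the SAP. This stands: the absence of an entry in SAP section 6 adds little, and the fault is within the SAP.
- **Week 16 is the primary time point.** A Week 16 model horizon would be defensible if it were stated and reasoned. It appears only in output titles and is shorter than the endpoint definition.

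A reader might also infer that the sponsor meant to keep reporting discretion. Nothing in the documents shows that, and an incomplete update explains the text equally well.

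**Conclusion.** The point holds as an internal inconsistency of the SAP, of minor weight. Its size is two of seven endpoint visits without a between-arm comparison for three exploratory analytes, plus an unresolved statement on whether those analytes belong in the CSR. They lie outside the hierarchical test in SAP 4.1.1, so type I error, power and the primary result are unaffected. The conclusion assumes that the Appendix C titles set the model horizon, since 4.2.8.2 gives none, and that section-14 numbering denotes CSR outputs.

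Three stronger readings are tempting and are not supported:

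- **That the trial could not show whether suppression reverses.** Descriptive summaries of these cytokines are planned at both follow-up visits, and other markers are formally compared through Week 24.
- **That the omitted visits are off-drug.** They are post-dosing. The donation rule in protocol 5.3 equates 16 weeks with five half-lives, or 16/5 = 3.2 weeks each. Under simple first-order decay from the last dose, 2^−(8/3.2) = 18% and 2^−(12/3.2) = 7% would remain.
- **That loss of effect would show mainly at those visits.** Residual drug is not biomarker effect, and the documents give no concentration-response relation for these cytokines.

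**What to change.** Make two edits to the SAP before the primary analysis lock.

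1. Extend Tables 14.2.21.2, 14.2.22.2 and 14.2.24.2 and their figures from Week 16 to Week 24, and name that horizon in 4.2.8.2, so that the comparison matches the endpoint. If the sponsor prefers Week 16 for the model, 4.2.8.2 should say so and give the reason.
2. Settle the CSR status. Either remove the asterisks from serum IL-5, IL-13 and TSLP in Table 1, which fits the January 2023 addition of these analyses, or keep them and state in 4.2.8.2 and Appendix C that these outputs are reported outside the CSR. The documents do not show which was intended; either is consistent.

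The cost is SAP wording and a changed visit cut in three models and their figures. Sampling and analysis windows are already in place. The small downside is that SV11 and SV12 assay results must be available by the final analysis.
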